3.3.1.2 Handling of Missing Data

In general, missing data will not be imputed and will be treated as missing unless specifically described in an analysis section. The following considerations are made for missing safety data, adverse event (AE) dates, and concomitant medication/diseases dates:

- Safety assessment values of the form ‘<x’ or ‘>x’ (i.e., above or below the limits of quantifications) will be imputed as ‘x’ divided by the square root of 2 in the calculation of summary statistics but displayed as ‘<x’ or ‘>x’ in the listings.
- AEs that have missing causality after data querying will be assumed to be related to study drug.
- For missing AE start dates, the following will be applied:
 - Only partial AE start dates are imputed. Dates which are completely missing are not imputed.
 - If only the day is missing and the month and/or the year is different from the month and year of the first dose of investigational product (IP), assume 01-MMM-YYYY. If the month and year are the same as the first dose of IP month and year and the end date is on or after (including ongoing / missing) the first dose of IP, then assume the date of the first dose of IP. If the month and year are the same as the first dose of IP month and year and the end date is prior to the first dose of IP, then assume the end date.

- If the month is missing and the year is different from the year of first dose of IP, assume 01-JAN-YYYY of the collected year. If the year is the same as the first dose of IP year and the end date is on or after (including ongoing / missing) the first dose of IP, then assume the date of the first dose of IP. If the year is the same as the first dose of IP and the end date is prior to the first dose of IP, then assume the end date.
- After applying these rules, if the imputed AE start date is after a complete AE end date then assume the same date as the complete AE end date; if the end date is missing and the imputed AE start date is after the end of study date then assume the same date as the study end date.
- For missing AE end dates, the following will be applied:
 - Completely missing AE end dates are not imputed.
 - If the AE is ongoing, the end date is set to missing.
 - If the AE is not ongoing, and if only the day is missing then assume the last day of the collected month.
 - If the AE is not ongoing, and both, the day and the month are missing then assume 31-DEC of the collected year.
 - After applying these rules, if the imputed AE end date is after the end of study date or the date of death, the AE end date is set to the earliest date between the end of study date and the date of death.
- For missing concomitant medication and concomitant procedures start dates, neither partially nor completely missing dates are imputed.
- For missing concomitant medication and concomitant procedures end dates, the following will be applied:
 - Completely missing end dates or dates for which the year is missing are not imputed.
 - If the concomitant medication is ongoing, the end date is set to missing.
 - If the concomitant medication / procedure is not ongoing, and if only the day is missing then assume the last day of the collected month.

- If the concomitant medication / procedure is not ongoing, and both, the day and the month are missing then assume 31-DEC of the collected year.
- After applying these rules, if the imputed date is after the end of study date or the date of death, the concomitant medication / procedure end date is set to the earliest date between the end of study date and the date of death.
- If a subject is known to have died where only a partial death date is available, then the date of death will be imputed as the latest of the last known date to be alive + 1 from the database and the death date using the available information provided:
 - Missing day only: Use the 1st of the month.
 - Missing day and month: Use 1st January.
 - Missing year: Impute the year of dosing.

For all missing start/end dates, flags will be retained in the analysis datasets indicating where any programmatic imputation has been applied, and in such cases, any durations would not be calculated.

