3.3.1.2 Handling of Missing Data

In general, missing data will not be imputed and will be treated as missing unless specifically described in an analysis section. The following considerations are made for missing safety data, adverse event (AE) dates, and concomitant medication/diseases dates:

- Safety assessment values of the form ‘<x’ or ‘>x’ (i.e., above or below the limits of quantifications) will be imputed as ‘x’ in the calculation of summary statistics but displayed as ‘<x’ or ‘>x’ in the listings.
- Adverse events that have missing causality after data querying will be assumed to be related to study drug.
- For missing AE/concomitant medication/disease start dates, the following will be applied:

- Missing day: Impute 1st of the month unless the month is the same as that of the first dose of study drug in which case impute first dose date.
- Missing day and month: Impute 1st January unless the year is the same as that of the first dose date in which case impute first dose date.
- Missing year: Impute the year of dosing.
- Completely missing: Impute first dose date unless the end date suggests it could have started prior to this in which case impute 1st January of the same year as the end date.
- For missing AE/concomitant medication/disease end dates, the following will be applied:
 - Missing day: Impute the last day of the month unless the month is the same as that of the last dose of the study drug in which case impute the date of last dose.
 - Missing day and month: Impute 31st December unless the year is the same as that of the last dose of study drug in which case impute date of last dose.
 - Missing year: Impute the year of dosing.
 - Completely missing: Do not impute a date i.e., assume that AE/concomitant medication/disease is ongoing.

For all missing start/end dates, flags will be retained in the analysis datasets indicating where any programmatic imputation has been applied, and in such cases, any durations would not be calculated.

If a subject is known to have died where only a partial death date is available, then the date of death will be imputed as the latest of the last known date to be alive + 1 from the database and the death date using the available information provided:

- Missing day only: Use the 1st of the month.
- Missing day and month: Use 1st January.
- Missing year: Impute the year of dosing.

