3.3 General Considerations

The following principles will be followed throughout the study:

- Continuous variables will be summarized by the number of non-missing observations, mean, standard deviation (SD), median, first and third quartiles, and the minimum and maximum as appropriate.
- Log-transformed continuous variables will be summarized in a similar manner. In addition, the relative change from baseline will be calculated by back-transforming the change from baseline of the logarithmic variable as necessary.
- Categorical variables will be summarized as counts (n) and percentages (%). Unless otherwise stated, percentages will be calculated using the relevant analysis set population total as the denominator. Percentages will not be presented for zero counts.
- Mean and medians will be rounded to one additional decimal place relative to the original data, the SD will be rounded to two additional decimal places, and the maximum, minimum and quartiles will be displayed with the same accuracy as the original data. 95% confidence intervals (CIs) will be presented to one more decimal place than the raw data. Percentages (proportion) will be rounded to one decimal place.
- Summaries will be provided by time point of assessment where appropriate. Where summaries are over time, study day will be calculated in relation to Day 1, the date of first dose of study treatment.

- Corresponding listings will be provided for all tabulated results unless stated otherwise. Any additional listings that are required will be described in the appropriate sections of the SAP.
- Statistical tests will be performed using two-sided test at a 5% significance level, if not explicitly stated otherwise.
- SAS® version 9.3 or higher will be used for all data analyses.

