Follow-up period		
Week 12	Day 85	Day 71 – Day 91
Week 14	Day 99	Day 92 – Day 112
Week 18	Day 127	Day 113 – Day 140
Week 22	Day 155	Day 141 onwards

^a Baseline is defined as the last measurement prior to first dose of study treatment. Pre-dose values on Day 1 qualify as baseline measurements.

^b Day 1 is defined as date of first dose of study treatment. Includes all measurements collected at Day 1 after the first dose of IP.

Table 3: Analysis visit windows for anti AZD8233 antibodies

Analysis Visits	Scheduled visit day	Analysis visit window (days)
Baseline ^a	Day -28 to Day 1	≤ Day 1
Treatment period		
Day 1	Day 1	Day 1 ^b
Week 1	Day 8	Day 2 – Day 18
Week 4	Day 29	Day 19 – Day 42
Week 8	Day 57	Day 43 – Day 70
Follow-up period		
Week 12	Day 85	Day 71 – Day 98
Week 16	Day 113	Day 99 – Day 126
Week 20	Day 141	Day 127 – Day 154
Week 24	Day 169	Day 155 onwards.

^a Baseline is defined as the last measurement prior to first dose of study treatment. Pre-dose values on Day 1 qualify as baseline measurements.

^b Day 1 is defined as date of first dose of study treatment. Includes all measurements collected at Day 1 after the first dose of IP.

An early discontinuation visit (EDV) may take place at any point during the study up to Week 12. In this instance, follow-up visits (Week 2, Week 4 etc.) will begin at date of last administered treatment and performed every 2 weeks after last dose prior to study discontinuation. For those patients with an early discontinuation, an additional analysis visit window will be applied to follow-up visits as follows and will be used for the summary of safety and lab data.

If there is more than one value per subject within an analysis visit window then the closest value to the scheduled visit date will be summarized, or the later value if the values are equidistant from the nominal visit date, the remaining visits will be treated as ‘Unscheduled Visits’ Listings will display all values contributing to a time point for a subject and will highlight the value that contributed to the summary table where feasible.

For summaries showing the maximum or minimum values, the maximum/minimum value recorded on treatment will be used, regardless of where it falls in an interval. For summaries

at a subject level (i.e., the maximum) all values will be included regardless of whether they appear in a corresponding visit-based summary.

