4.2.1.2 Derivations

LDL-C values will be assigned to analysis visits as defined in Section 3.3.2. Measurements below the LLOQ for which the exact value cannot be determined will be replaced by the LLOQ divided by the square root of 2.

Change from baseline of the log-transformed variable will be calculated as the visit value in the natural logarithm minus the baseline value in natural logarithm.

Percent change will be derived from the MMRM estimates as:

$$\text{Mean percent change} = 100 * (\exp(\text{LSMean}) - 1)$$

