4.3.3 Clinical Laboratory, Blood Sample

4.3.3.1 Definitions and Derivations

In the assessments of hematology parameters, clinical chemistry and coagulation, the parameters to be summarized are listed in Appendix 7.2.

Clinical laboratory results will be assigned to analysis visits as described in Section 3.3.2.

Safety clinical laboratory results below the lower limit of quantification (LLOQ) for which the exact value cannot be determined will be replaced with the LLOQ.

After replacements of LLOQ, the change from baseline will be calculated for all post-baseline timepoints as the respective timepoint value minus the baseline value.

Based on the respective reference range indicators, the following flags will be applied to all laboratory assessments; 'Normal' (if the value is within the normal reference range), 'Low' (if the value is below the normal reference range) or 'High' (if the value is above the normal reference range).

eGFR

Subject's eGFR will be calculated from serum creatinine (SCr) concentration, according to the Japanese equation as follows:

$$\text{eGFR} = 194 \times \text{SCr}(\text{mg/dL})^{-1.094} \times \text{Age}^{-0.287} \times \alpha$$

where α is 1 for males and 0.739 for females.

Liver enzyme abnormalities

AST, ALT and TBL will be classified as follows:

AST and ALT:

- $<1.5 \times \text{ULN}$ (or below the LLOQ).
- ≥ 1.5 to $<3 \times \text{ULN}$.
- ≥ 3 to $<5 \times \text{ULN}$.
- ≥ 5 to $<8 \times \text{ULN}$.
- $\geq 8 \times \text{ULN}$.

TBL:

- $<1 \times \text{ULN}$ (or below the LLOQ).
- ≥ 1 to $<2 \times \text{ULN}$.
- $\geq 2 \times \text{ULN}$.

Occurrences of AST or ALT $\geq 3 \times \text{ULN}$ together with TBL $\geq 2 \times \text{ULN}$ are reported as SAE (Potential Hy's Law).

Platelet count

Platelet count will be classified as follows:

- $< \text{LLN}$
- $> \text{ULN}$

- < 50 ($10^9/L$)
- < 75 ($10^9/L$)
- < 100 ($10^9/L$)
- < 150 ($10^9/L$)
- > 30% decrease from baseline
- < 150 ($10^9/L$) and > 30% decrease from baseline

Shift to minimum value on-treatment value for platelet count will be classified as follows:

- < 50 ($10^9/L$)
- ≥ 50 and < 75 ($10^9/L$)
- ≥ 75 and < 100 ($10^9/L$)
- ≥ 100 and < 150 ($10^9/L$)
- ≥ 150 ($10^9/L$)

Missing data will not be imputed and only observed values will be reported in the summary tables and listings. Treatment discontinuation visit will be mapped according to Section 3.3.2.

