4.3.3.2 Presentation

Laboratory data will be summarized based on the Safety Analysis Set. Summaries of the individual values and change from baseline will be presented by treatment group and visit according to the principles outlined in section 3.3.1. The number and proportion of patients with liver enzyme abnormalities will be summarized by treatment group and visit including a summary of the maximum recorded post-baseline value. Treatment-emergent platelet count abnormalities will be summarised by treatment group and visit, including the shift to minimum value and key subject information will be presented.

Shift tables will be presented for select laboratory parameters (clinical chemistry and hematology). An additional shift table will be presented for hematology results, displaying the percent change from baseline (i.e. the relative change). Spaghetti plots over time will be produced for platelet count, ALT, AST, and TBL, with the corresponding reference range overlaid on top. The following additional plots will be presented for platelet count only:

- Empirical cumulative distribution function curves for the absolute change from baseline to minimum value.
- A spaghetti plot of the relative change from baseline in subjects with platelet count <150 ($10^9/L$) or $> 30\%$ decrease from baseline.
- A spaghetti plot of the absolute change from baseline in subjects with platelet count <150 ($10^9/L$) or $> 30\%$ decrease from baseline.

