3.3.1.2 Handling of Missing Data

In general, missing data will not be imputed and will be treated as missing unless specifically described in an analysis section. The following considerations are made for missing safety data, adverse event (AE) dates, and concomitant medication/diseases dates:

- Safety assessment values of the form ‘ $<x$ ’ or ‘ $>x$ ’ (i.e., above or below the limits of quantifications) will be imputed as ‘ x ’ in the calculation of summary statistics but displayed as ‘ $<x$ ’ or ‘ $>x$ ’ in the listings.
- Adverse events that have missing causality after data querying will be assumed to be related to study drug.
- For missing AE/concomitant medication/disease start dates, the following will be applied:
 - Missing day: Impute 1st of the month unless the month is the same as that of the first dose of study drug in which case impute first dose date.
 - Missing day and month: Impute 1st January unless the year is the same as that of the first dose date in which case impute first dose date.
 - Missing year: Impute the year of dosing.
 - Completely missing: Impute first dose date unless the end date suggests it could have started prior to this in which case impute 1st January of the same year as the end date.
- For missing AE/concomitant medication/disease end dates, the following will be applied:
 - Missing day: Impute the last day of the month unless the month is the same as that of the last dose of the study drug in which case impute the date of last dose.
 - Missing day and month: Impute 31st December unless the year is the same as that of the last dose of study drug in which case impute date of last dose.
 - Missing year: Impute the year of dosing.
 - Completely missing: Do not impute a date i.e., assume that AE/concomitant medication/disease is ongoing.

For all missing start/end dates, flags will be retained in the analysis datasets indicating where any programmatic imputation has been applied, and in such cases, any durations would not be calculated. When imputing missing/partial dates, programmatic checks will be done to ensure a future date has not been imputed.

If a subject is known to have died where only a partial death date is available, then the date of death will be imputed as the latest of the last known date to be alive + 1 from the database and the death date using the available information provided:

- Missing day only: Use the 1st of the month.
- Missing day and month: Use 1st January.

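### The Part B SAP enters safety results reported as `>x` in summary statistics at x/√2 = 0.707x, a value the result itself rules out

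*SAP*

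**What the plan says.** The first bullet of section 3.3.1.2 in the Part B SAP covers safety values of the form `<x` and `>x` together: "i.e., above or below the limits of quantifications) will be imputed as ‘x’ divided by the square root of 2". The rule applies to summary statistics; listings keep the reported `<x` or `>x`. Nothing in the bullet confines the division to `<x`.

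The matching bullet in section 3.3.1.2 of the Part A SAP reads "will be imputed as ‘x’ in the calculation of summary statistics but displayed as", with no division, and the Part C SAP has the same wording.

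The Part B section on blood laboratory data, 4.3.3.1, has its own replacement rule, but only at the lower end: "Safety clinical laboratory results below the lower limit of quantification (LLOQ) for which the exact value cannot be determined will be replaced with the LLOQ". Sections 4.3.4.1 (urinalysis) and 4.3.5.1 (other laboratory evaluations) say the same. None of the three has a rule for a result above an upper limit.

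The matching presentation sections (4.3.3.2, 4.3.4.2, 4.3.5.2) state that individual values and "change from baseline will be presented by treatment group and visit according to the principles outlined in section 3.3.1". Section 3.3.1 contains 3.3.1.2. Section 3.3 lists the statistics: "Continuous variables will be summarized by the number of non-missing observations, mean, standard deviation (SD), median, first and third quartiles, and the minimum and maximum".

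**The concern.** Dividing a limit by √2 is a substitution for a left-censored value. For `<x`, the figure x/√2 lies inside the possible range. For `>x` it lies outside it, so the rule replaces a right-censored result with a number known to be false.

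Elsewhere in Part B the division is used in that left-censored sense. For LDL-C, section 4.2.1.2 says "Measurements below the LLOQ for which the exact value cannot be determined will be replaced by the LLOQ divided by the square root of 2". Its extension to `>x` safety values therefore looks like a drafting slip. Neither the Part B amendment history nor its list of changes to the protocol-planned analyses explains why Part B differs from Parts A and C. Part C Edition 2.0, dated after Part B Edition 2.0, still imputes x.

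The error pulls a high extreme down, which is the unhelpful direction for a safety table. A participant at `>x` would rank below participants with quantified results between 0.707x and x, and a by-visit maximum could be printed below x while the listing shows `>x`.

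**Working it through.** The plan states no figure to reproduce here. The check is arithmetic on the stated rule.

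**Inputs**
- Imputed value for `>x` in Part B: x/√2 (Part B SAP 3.3.1.2).
- Imputed value for `>x` in Parts A and C: x (their section 3.3.1.2).
- Arm size: about 60 randomised 1:1:1 (protocol 4.1 and 9.2), so 60/3 = 20 per arm.
- Number of `>x` results per arm and visit: not stated, so k is left free.

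**Shortfall per value**
- 1/√2 = 0.7071, so `>10` enters as 7.07, `>100` as 70.7 and `>1000` as 707.
- 1 − 0.7071 = 0.2929. The true value exceeds x, so the entry is at least 29.3% too low.

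**By-visit mean**, compared with entering x: shift = k × 0.2929x / 20.

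| k | Fall in arm mean |
|---|---|
| 1 | 0.0146x |
| 2 | 0.0293x |
| 4 | 0.0586x |

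The true shortfall is larger, because x is itself only a lower bound.

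**By-visit maximum.** If every quantified result in the arm is below x, the printed maximum is the larger of 0.707x and the highest quantified result. Either way it is below x.

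**Quartiles.** These need not move. With 20 values, taking one top-ranked value from x to 0.707x leaves the third quartile unchanged if that quartile is already below 0.707x. It can fall if the quartile lies above 0.707x.

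**Change from baseline (conditional).** If 0.707x is carried into the change, then with assumed baselines:
- 0.75x: 0.7071x − 0.75x = −0.043x, instead of x − 0.75x = +0.25x.
- 0.90x: 0.7071x − 0.90x = −0.193x, instead of x − 0.90x = +0.10x.

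The SAP leaves this open. Sections 4.3.3.1, 4.3.4.1 and 4.3.5.1 derive the change after LLOQ replacement and do not mention `>x`, while the presentation sections send its summary to 3.3.1.

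**The case against.** The best textual defence is in 4.3.3.1, which also says that missing laboratory data are left unimputed and that tables show observed values. Section 3.3.1.2 places the `<x`/`>x` rule among considerations for missing safety data, so 4.3.3.1 might be read as switching it off for blood samples. That reading does not hold. The same section replaces results below the LLOQ, so its sentence on missing data cannot be meant for reported censored results. Sections 4.3.4.1 and 4.3.5.1 do not contain the sentence at all.

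The reference to 3.3.1 may be a slip for 3.3, where the summary principles sit. That is plausible, and it makes the cross-reference weak evidence. The bullet in 3.3.1.2 still applies on its own terms.

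The reach is narrow, and this part of the objection stands. Four stronger readings are tempting, and the documents do not support them:
- A reader might infer that every summary statistic must be biased. Only the mean necessarily falls.
- A reader might infer that overall on-treatment maxima are certainly affected, or certainly safe. Section 3.3.2 says "For summaries showing the maximum or minimum values, the maximum/minimum value recorded on treatment will be used". That rule concerns visit windows and assigns no number to a censored result, so it settles neither.
- A reader might infer that participant-level safety decisions are compromised. The discontinuation criteria in protocol 7.1 apply to participants' own results, not to SAP summary tables, and listings keep `>x`.
- A reader might infer an effect on efficacy. The bullet covers safety values; the primary LDL-C analysis has its own rule in 4.2.1.2, for results below the LLOQ.

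**Conclusion.** The point holds and is minor. The Part B rule for `>x` is wrong whenever it applies, because it assigns a value that the result excludes, and it departs without explanation from Parts A and C. Each such value lowers the by-visit arm mean by 0.0146x relative to entering x, assuming about 20 participants contribute per arm. The by-visit maximum, and possibly the quartiles, can be too low. Whether overall maxima and change from baseline are affected cannot be determined from the text. The practical effect depends on how many `>x` safety results occur. The documents do not give that number, and if it is zero no `>x` figure changes.

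**What to change.** In the first bullet of Part B SAP 3.3.1.2, delete the seven words that divide x by the square root of 2. Safety values of the form `>x` are then set to x, as in Parts A and C. Values of the form `<x` are set to the limit, which also removes the present conflict with the LLOQ rule in 4.3.3.1, 4.3.4.1 and 4.3.5.1. Add a clause stating that the same value is used for change from baseline and for maxima. Keep LLOQ/√2 for lipids only. Setting `>x` to x still understates the true value, so the bias is reduced, not removed.

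The cost is one edited sentence and one added clause. Any safety summary already produced that contains a `>x` or `<x` value entered at x/√2 would need rerunning.

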8.3.1 Time Period and Frequency for Collecting AE and SAE Information

Adverse events will be collected from time of first dose throughout the treatment period and including the follow-up period.

SAEs will be recorded from the time of signing of the informed consent form.

If the Investigator becomes aware of an SAE with a suspected causal relationship to the study intervention that occurs after the end of the clinical study in a participant treated by him or her, the Investigator shall, without undue delay, report the SAE to the sponsor.

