9.2 Sample Size Determination

[Part A / Part C]

Due to the exploratory nature of the study, the sample size is not based on formal statistical considerations, but on experience from similar Phase I studies previously conducted with other compounds. Eight Japanese subjects on active drug are considered to be sufficient to confirm a tendency for safety, PK, and PD data.

[Part B]

The primary endpoint is assumed to follow a log-normal distribution with a standard deviation of 0.3. Under these assumptions, at least 18 evaluable patients per arm yield more than 95% power to detect a difference of 0.693 on the log-scale (corresponding to 50% relative reduction) compared to placebo in a two-sided t-test at a 5% significance level. The same number of evaluable patients would provide approximately 89% power to detect a difference of 0.33 between the **CCI** group and **CCI** group. Accounting for 10% drop-out, 60 patients in total will be randomized.

Note: “Enrolled” means a participant’s, or their legally acceptable representative’s, agreement to participate in a clinical study following completion of the informed consent process. Potential participants who are screened for the purpose of determining eligibility for the study, but are not randomly assigned/assigned in the study, are considered “screen failures”, unless otherwise specified by the protocol.

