4.3.2 Adverse Events

4.3.2.1 Definitions and Derivations

An adverse event (AE) is the development of any untoward medical occurrence in a patient or clinical study participant administered a medicinal product and which does not necessarily have a causal relationship with this treatment. An AE can therefore be any unfavourable and unintended sign (eg, an abnormal laboratory finding), symptom (for example nausea, chest pain), or disease temporally associated with the use of a medicinal product, whether or not considered related to the medicinal product.

The term AE is used to include both serious (SAE) and non-serious AEs and can include a deterioration of a pre-existing medical occurrence. An AE may occur at any time, including run-in or washout periods, even if no study intervention has been administered.

A treatment-emergent adverse event (TEAE) is defined as an AE with an onset date on or after the first dose date.

Adverse events will be coded using the MedDRA version 24.0 or higher.

Imputation of partial dates and handling of missing data will be conducted as defined in Section 3.3.1.2.

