4.3.2.2 Presentation

All summaries of adverse event data will be based on the Safety Analysis Set and will be presented by treatment group. Summary tables will include TEAEs only whereas listings will include all reported AEs.

A subject-level overview of AEs (the number and percent of subjects and the number of events) will be tabulated by the treatment groups in a single table for:

- Any AE.
- AEs possibly related to study treatment.
- AEs with an outcome of death.
- AEs with outcome of death possibly related to study treatment.
- All serious adverse events (SAE).
- SAEs possibly related to study treatment.

- AEs leading to discontinuation of study treatment.
- AEs leading to discontinuation of study treatment, possibly related to study treatment.
- AEs leading to dose interruption.
- AEs leading to withdrawal from the study.

Separate AE summary tables of the number and percentage of subjects with AEs and the number of events in each of the categories above will be produced by SOC and PT.

Additionally, the following tables will be presented by SOC and PT:

- AEs by the maximum reported intensity.
- AEs by causality assessment.
- Bleeding AEs (Haemorrhages (SMQ) including both "Haemorrhage laboratory terms (SMQ)" & "Haemorrhage terms (excluding laboratory terms) (SMQ)").

Subjects with multiple events in the same category are counted once in that category.

Subjects with events in more than one category are counted once in each of those categories.

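### In Part B, an adverse event with no recorded start date cannot qualify as treatment-emergent, so it drops out of the AE summary tables and is seen only in the listings

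*SAP*

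**What the plan says.** Three sentences of the Part B SAP act together.

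- Section 3.3.1.2, on AE start dates: "Only partial AE start dates are imputed. Dates which are completely missing are not imputed".
- Section 4.3.2.1: "A treatment-emergent adverse event (TEAE) is defined as an AE with an onset date on or after the first dose date".
- Section 4.3.2.2: "Summary tables will include TEAEs only whereas listings will include all reported AEs".

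On what is collected, protocol 8.3.1 states: "Adverse events will be collected from time of first dose throughout the treatment period and including the follow-up period". The same section has SAEs recorded from the signing of consent.

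The Part A and Part C SAPs define a treatment-emergent AE (TEAE) in the same way and also tabulate TEAEs only. Their section 3.3.1.2, however, has a different rule for a start date that is wholly absent: "Completely missing: Impute first dose date unless the end date suggests it could have started prior to this". Where the end date does suggest an earlier start, they use 1 January of the end-date year.

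**The concern.** A missing date cannot be shown to fall on or after another date. A Part B event without a start date therefore fails the TEAE definition and leaves the overview table and the tables by system organ class and preferred term. These include the tables for serious events, related events, events leading to discontinuation and bleeding events.

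For a non-serious event this exclusion goes against the collection rule, because such events are solicited only after dosing starts. The missing date says nothing that should take the event out of the on-treatment count.

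Part B is the part with a control group of useful size: 60 participants randomised 1:1:1, against about 3 placebo participants in each of Parts A and C. Its Week 12 analysis is also meant to inform the Phase 3 plan (SAP Part B 3.1). An avoidable undercount in its AE tables is worth removing.

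**Working it through.** The plan gives no figure on this point, so there is none to reproduce. The check has three parts.

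**1. Does any other Part B text keep the event in the tables?** The AE section gives no rule of its own and refers back: "Imputation of partial dates and handling of missing data will be conducted as defined in" section 3.3.1.2. Section 3.3.1.3 assigns listed events to a study period after dates have been imputed, and has no provision for an event still undated. Section 2, on changes to the protocol's planned analyses, does not mention the matter. Nothing found restores the event.

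The rule for partial dates in 3.3.1.2 goes the other way. If only the year is known, that year is the year of first dose, and the event is ongoing, has no end date or ended on or after first dose, then onset becomes the first dose date. An ongoing event known only to that year is tabulated; an ongoing event with no year at all is not.

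**2. How do the three SAPs treat the same record?** Take a completely missing start date and apply each SAP's date rule, then the common test (onset date on or after first dose date). The A/C exception can be read narrowly (only an end date before first dose triggers it) or broadly (any known end date may trigger it).

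| End date of the event | Part B: TEAE? | Parts A/C, narrow | Parts A/C, broad |
|---|---|---|---|
| Missing or ongoing | No | Yes | Yes |
| After first dose, same calendar year | No | Yes | No |
| After first dose, next calendar year | No | Yes | Yes |
| Before first dose | No | No | No |

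In the second row the broad reading sets onset to 1 January of the dosing year, before first dose. In the third row, 1 January of the following year is after first dose. Part B excludes the event in all four cases. Parts A and C exclude it in the fourth, and in the second only on the broad reading.

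**3. Size.** Protocol 9.2 states: "Accounting for 10% drop-out, 60 patients in total will be randomized". With 1:1:1 allocation:

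- Participants per arm: 60/3 = 20.
- Largest change in an arm's incidence per record: 1/20 = 5.0 percentage points.
- Largest change for the two active arms pooled: 1/40 = 2.5 percentage points.

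These are maxima. Participants are counted once per category, so the percentage moves only if the participant has no other event in that row.

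**The case against.** The best defence is that the trigger is very narrow. The rule applies only when the whole start date is absent. Start date and time are among the variables collected for each AE (protocol 8.3.2), and events are elicited by asking about health problems since the last contact (8.3.4), at visits one to two weeks apart. Onset will nearly always be bracketed. This stands: such records are likely to be rare, and the documents give no count.

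A second defence is that leaving the date blank follows the general default: "In general, missing data will not be imputed and will be treated as missing unless specifically described in an analysis section". That explains the rule but not its effect, because the TEAE filter turns an unknown date into an exclusion. A reader might also see a contradiction with the Part B rule that missing causality counts as related. It is a difference in approach between two fields, not a contradiction.

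Several stronger readings are tempting but not supported:

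- That the event is lost altogether. It stays in the listings, which carry all reported AEs.
- That it leaves every table. The injection site reaction table (SAP Part B 4.2.7.4) does not repeat the TEAE restriction, so its loss there is uncertain.
- That AZD8233 always looks safer as a result. The rule is the same in all three blinded arms, and losing a placebo event would make the active arms look relatively worse.
- That Parts A and C always count such an event. Their end-date exception can place onset before first dose.
- That every undated event is post-dose by design. This holds for non-serious events only, since SAEs are recorded from consent.

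**Conclusion.** The point holds for Part B. As written, an AE with a completely missing start date is left out of the AE summary tables and appears only in the listings. The exclusion is not stated in words; it follows from combining the date rule, the TEAE definition and the restriction of the tables to TEAEs. For non-serious events it conflicts with the protocol's collection window, and it differs from the default in Parts A and C.

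The reported incidence in the affected arm can only fall, while the difference between arms has no fixed direction. The 5-point maximum per record assumes 20 participants in the arm's safety analysis set; a smaller set gives a slightly larger step. The expected overall effect is small because few such records are likely. The primary LDL-C analysis is not touched. This is a cheap correction to safety reporting, not a threat to the trial's conclusions.

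**What to change.** Change Part B only. Add to SAP Part B 3.3.1.2 that an AE whose start date is completely missing is counted as treatment-emergent, with its start date set to the first dose date and flagged as imputed, unless its end date is before first dose.

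The cost is one sentence and one line of derivation code; 3.3.1.2 already provides for imputation flags. There is no need to rewrite the Part A SAP, whose current edition postdates database lock, or the Part C SAP.

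The downside is that an undated SAE that began before dosing would be counted as treatment-emergent if it has no end date or ended after first dose. The flag lets a reader pick out such a case in the listings.
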